6.3 Urgent Target Vessel Revascularization

Urgent Target Vessel Revascularization (uTVR) is either a PCI following the index PCI or any CABG procedure performed after the index PCI on a non-selective basis in the target vessel because of recurrent myocardial ischemia. A revascularization procedure in the target vessel is considered urgent if it is due to one or more episodes of chest pain, presumed to be ischemic in origin and lasting at least 5 minutes, and results in either urgent repeat PCI or urgent coronary artery bypass surgery involving the target vessel. In the absence of pain, new ischemic ST-segment or T-wave changes, acute pulmonary edema, ventricular arrhythmias presumed to be ischemic in origin will constitute sufficient evidence of ischemia. The episode of ischemia leading to urgent repeat PCI must occur following completion of the index PCI and guidewire removal.

For uTVR to count towards the primary composite endpoint, uTVR will have to be initiated during the course of the study (i.e., 48 hours following PCI or hospital discharge, whichever comes first).

uTVR will not be adjudicated.

7.0 SAFETY MEASUREMENTS

The following adverse events will be monitored closely from study drug administration through 48 hours following PCI or hospital discharge, whichever comes first.

7.1 Bleeding

Bleeding complications will be closely monitored clinically and by serial determinations of hemoglobin and hematocrit. All bleeding events from study drug administration through 48 hours following PCI or hospital discharge, whichever comes first, will be collected and categorized by site and quantified according to REPLACE-2 Major bleeding criteria. While other bleeding definitions will also be applied, REPLACE-2 Major bleeding criteria will be

used in the primary safety analysis and in the bleeding component of the primary composite endpoint.

Hemoglobin, hematocrit and platelet count will be sampled at the same times as the troponin draws. i.e., immediately prior to PCI, preferably from the PCI access sheath or guiding catheter, and at 9 ± 3 hours following PCI, and at 21 ± 3 hours. If the patient remains in the hospital longer than 36 hours after PCI, a third hemoglobin, hematocrit and platelet count post-PCI draw will be sampled at 42 ± 6 hours after PCI.

Bleeding events will not be adjudicated.

7.1.1 Bleeding Site

Each site will be recorded on the CRF and evaluated separately. Bleeding sites include intracranial, retroperitoneal, sheath puncture site, other puncture site, ENT bleed, GI bleed, GU bleed, cardio/pulmonary bleed, other, and unknown. Microscopic hematuria and positive fecal occult blood will be recorded as laboratory adverse events only and will not be captured as bleeding events. Information on whether the bleeding event was a result of CABG will be collected on the CRF.

7.1.2 Primary Safety Measurement Non-CABG REPLACE-2 Major Bleeding Definition

Major bleeding is defined using the criteria from the REPLACE-2 trial. Major bleeding is defined as follows [57]:

- a. transfusion of ≥ 2 units whole blood or packed red blood cells, or
- b. intracranial hemorrhage, or
- c. retroperitoneal hemorrhage, or
- d. a fall in Hgb < 4 g/dL (or 12% of Hct) with no bleeding site identified despite attempts to determine, or
- e. spontaneous or non-spontaneous blood loss associated with a Hgb drop > 3 g/dL (or 10% of Hct) with an overt site of hemorrhage.

The REPLACE-2 Major bleeding definition takes into account blood transfusions, so that hemoglobin and hematocrit values are adjusted by 1 g/dl or 3%, respectively, for each unit of blood transfused.

Therefore, the true change in hemoglobin or hematocrit if there has been an intervening transfusion between two blood measurements is calculated as follows [68]:

Δ Hemoglobin = [baseline Hgb - post-transfusion Hgb] + [number of transfused units];

Δ Hematocrit = [baseline Hct - post-transfusion Hct] + [number of transfused units x 3].

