A second challenge with GPIIb/IIIa inhibitor therapy is their extended infusion duration after the initial bolus. The long duration of infusion has several disadvantages such as an increase in bleeding tendencies, increased cost of therapy and the need for overnight hospitalization. Bleeding is an increasing concern for interventional cardiologists since it is associated with worse short- and long-term outcomes, including higher rates of mortality, compared with those who do not experience bleeding complications [27]. One possible solution to lower the bleeding risk associated with GPIIb/IIIa inhibitor therapy is to use a shortened infusion duration. This strategy is particularly attractive given today's PCI practice patterns for several reasons. First, patients today have superior oral antiplatelet medication with the combination of aspirin and clopidogrel, prasugrel or ticagrelor compared to aspirin only protection used in the early GPIIb/IIIa inhibitor clinical studies. With today's more potent oral antiplatelet therapies, patients undergoing PCI reach and sustain a greater degree of platelet inhibition in the immediate post-procedural period. A GPIIb/IIIa inhibitor infusion may therefore be needed for a shorter period following PCI. Second, PCI has evolved over the past 15 years to the point where it is a more common and routine procedure conducted over a shorter period of time. Shorter GPIIb/IIIa infusion durations are becoming increasingly popular and there is increasing demand for optimizing the duration of infusion. Fung and colleagues assessed the safety and efficacy of a bolus plus up to 2h eptifibatide infusion in nonemergent and uncomplicated PCI

versus a bolus plus up to 18h eptifibatide infusion [28]. Rates of REPLACE-2 major bleeding were found to be less frequent in the <2h group (1.0% vs. 4.2%; p=0.02) and the incidence of periprocedural myonecrosis (defined as troponin-I ≥ 3 x ULN) was non-inferior between the two groups (30.1% in the <2h group vs. 28.3% in the 18h group; p<0.012 for noninferiority). The authors concluded following uncomplicated PCI, eptifibatide infusion can be abbreviated safely to <2h [28].

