7.1.3.2 TIMI Minor Bleeding Definition

Minor bleeding is defined using the criteria from the trials of Thrombolysis in Myocardial Infarction (TIMI criteria). Minor bleeding is defined as follows [64]:

- a. If there is an observed blood loss and a drop in hemoglobin of 3 to 5 g/dl (or in hematocrit from 10% to 15%) from study entry to the time of the lowest hemoglobin (hematocrit); or
- b. if there was spontaneous gross hematuria or hematemesis (>120 mL), even if the hemoglobin or hematocrit drop was less than 3 g or less than 10%, respectively; or
- c. if there was an unobserved blood loss 4 g/dl or more in hemoglobin or 12% or more in hematocrit.

The TIMI Minor bleeding definition takes into account blood transfusions, so that hemoglobin and hematocrit values are adjusted by 1 g/dl or 3%, respectively, for each unit of blood transfused.

Therefore, the true change in hemoglobin or hematocrit if there has been an intervening transfusion between two blood measurements is calculated as follows [68]:

Δ Hemoglobin = [baseline Hgb - post-transfusion Hgb] + [number of transfused units];

Δ Hematocrit = [baseline Hct - post-transfusion Hct] + [number of transfused units x 3].

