- a. transfusion of ≥ 2 units whole blood or packed red blood cells, or
 - b. intracranial hemorrhage, or
 - c. retroperitoneal hemorrhage, or
 - d. decrease in Hgb more than 4 g/dL (or 12% of Hct) with no bleeding site identified despite attempts to determine, or
 - e. spontaneous or non-spontaneous blood loss associated with a Hgb drop > 3 g/dL (or 10% of Hct) with an overt site of hemorrhage.

The REPLACE-2 Major bleeding definition takes into account blood transfusions, so that hemoglobin and hematocrit values are adjusted by 1 g/dl or 3%, respectively, for each unit of blood transfused.

Therefore, the true change in hemoglobin or hematocrit if there has been an intervening transfusion between two blood measurements is calculated as follows:

- Δ Hemoglobin = [baseline Hgb - post-transfusion Hgb] + [number of transfused units];
- Δ Hematocrit = [baseline Hct - post-transfusion Hct] + [number of transfused units x 3].

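### The protocol reverses the hemoglobin inequality in the no-site REPLACE-2 Major bleeding criterion, the SAP states the opposite, and neither document says which text governs

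*Protocol*

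**What the plan says.** Protocol 7.1.2 lists five alternative ways to meet REPLACE-2 Major bleeding. The fourth, criterion (d), is "a fall in Hgb < 4 g/dL (or 12% of Hct) with no bleeding site identified despite attempts to determine". The identical line appears as criterion (d) of REPLACE-2 Plus Major in protocol 7.1.3.4.

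SAP 2.9.1.3 restates REPLACE-2 Major for the composite. Its criterion (d) is "decrease in Hgb more than 4 g/dL (or 12% of Hct) with no bleeding site identified despite attempts to determine".

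Under protocol 7.1, REPLACE-2 Major is "used in the primary safety analysis and in the bleeding component of the primary composite endpoint". The same section adds: "Bleeding events will not be adjudicated". SAP 3.10.1 confirms REPLACE-2 Major as a component of the primary composite.

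Protocol 7.1.3 places the alternate bleeding definitions, REPLACE-2 Plus among them, outside the primary safety analysis and the composite. SAP 2.9.2 names REPLACE-2 Plus Major as a safety measure but does not write out its criteria.

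**The concern.** The same criterion points in opposite directions in the two documents. Read literally, the protocol would count a trivial no-site fall as a major bleed and would refuse a large one on the hemoglobin limb. This sits in a component of the primary composite and in the primary safety endpoint, with no adjudication committee to catch a literal application.

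Nothing in either document settles the conflict. Protocol 9.0 leaves statistical methodology to the SAP but does not mention endpoint definitions. SAP section 1 says its analyses follow the protocol. The precedence rule in SAP 3.1.1 works only between parts of the SAP. The SAP change history (section 5) lists only analysis conventions, so the different wording is not presented as a deliberate change.

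**Working it through.** **Planned size.** The disputed item is a definition, so there is no stated figure to reproduce for it. The sample size does not depend on it. With a 51% rate in both arms, a 19.1-point margin, one-sided alpha 0.025 and 99% power (protocol Synopsis), n per arm = (1.960 + 2.326)² × 2 × 0.51 × 0.49 / 0.191² = 251.7, so 252 per arm or 504 in total, against the stated figure of about 500. Correcting the inequality changes none of these inputs.

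**Side by side.** Take a patient with no bleeding site found and no transfusion, judged on hemoglobin alone:

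| Fall in Hgb (g/dL) | Protocol 7.1.2(d), literal | SAP 2.9.1.3(d) | TIMI Minor (c) | TIMI Major |
|---|---|---|---|---|
| 1.0 | major | not major | not met | not met |
| 2.0 | major | not major | not met | not met |
| 3.9 | major | not major | not met | not met |
| 4.0 | not major | not major | met | not met |
| 4.1 | not major | major | met | not met |
| 5.0 | not major | major | met | met |

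The two REPLACE-2 columns agree only at exactly 4.0.

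**Which sign is wrong.** The protocol answers this without any outside source.

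- Criterion (e) of the same definition is "spontaneous or non-spontaneous blood loss associated with a Hgb drop > 3 g/dL (or 10% of Hct) with an overt site of hemorrhage". It would be incoherent to ask for more than 3 g/dL when a site is visible and accept 1 g/dL when none can be found.
- TIMI Minor (c) in protocol 7.1.3.2 sets a minimum for the parallel situation: "if there was an unobserved blood loss 4 g/dl or more in hemoglobin or 12% or more in hematocrit".
- TIMI Major in protocol 7.1.3.1 starts at a 5 g/dL reduction. Literally, a 5 g/dL no-site fall is TIMI Major yet fails REPLACE-2 Major (d) on hemoglobin, while a 1 g/dL fall passes.
- The transfusion rule in 7.1.2 says "hemoglobin and hematocrit values are adjusted by 1 g/dl or 3%, respectively, for each unit of blood transfused". At that rate 12% / 3% per g/dL = 4.0 g/dL. The paired hematocrit figure therefore confirms the threshold of 4; the other comparisons fix the direction.

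**Hematocrit limb.** Neither version of (d) gives the 12% its own sign, so it takes its direction from the hemoglobin wording before it. In the protocol it is therefore also unclear or reversed.

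**The non-CABG restriction.** The protocol Synopsis applies it twice: under Efficacy Measurements to the bleeding component of the composite, and under Safety Measurements to the primary safety endpoint. The title of 7.1.2 repeats it. SAP 2.9.1.3 and 2.9.2 do not contain it. The SAP therefore has the workable direction in (d) but is not the more complete text for the definition as a whole.

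**The case against.** The strongest reply is that the slip is obvious and harmless: the SAP specifies the primary analysis, its direction is workable, and the protocol's neighboring criteria make the intent plain. For the composite this largely stands, since nothing shows that the literal protocol text was ever applied. It does not settle which text was or will be used to classify individual bleeds.

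A second reply is that criterion (d) requires a failed search for a site, so routine small falls that nobody investigated would not qualify. That also stands and limits over-counting under the literal text. It does nothing for falls above 4 g/dL, which the literal text would stop counting on hemoglobin.

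An error in converting the PDF to text cannot be fully excluded, but the same sign appears in two separate protocol sections while nearby inequality signs read correctly.

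For REPLACE-2 Plus, there is an indirect route to the intended rule: 7.1.3.4 says it uses the REPLACE-2 criteria apart from transfusion, and the SAP gives criterion (d) in the workable direction. That is fair, but a rule reached by inference is weaker than a written one.

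Three stronger readings are tempting and are not supported.

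- A reader might infer a specific inflation of the false non-inferiority rate. That needs, by arm, the frequency of no-site falls below 4 g/dL among otherwise event-free patients and of the larger falls no longer counted. The documents give neither. The 1.0% and 4.2% rates in protocol 1.3 cover all REPLACE-2 Major criteria in a different study, of eptifibatide infusion durations. The direction is not fixed either: adding similar proportions of false events in both arms would dilute a difference, while unequal proportions could push it either way.
- A reader might infer that the REPLACE-2 Plus error also reaches the composite or directly contradicts the SAP. Protocol 7.1.3 keeps it out of both key endpoints, and the SAP has no written criteria for it to contradict.
- A reader might conclude that the SAP definition should simply govern throughout. That would drop the non-CABG restriction that the Synopsis applies to both uses.

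**Conclusion.** The contradiction is certain on the text, and the protocol's own definitions show that its sign is the reversed one. It affects one of five alternative criteria of REPLACE-2 Major, which is the primary safety endpoint and one component of the primary composite.

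Its effect on the composite is nil if the SAP wording is used for every patient, and otherwise unknown. No numerical estimate of bias or type I error is justified. The planned sample size is unaffected.

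REPLACE-2 Plus Major is a separate, lesser error: safety only, but with the reversed text as its sole written definition.

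This should be corrected before analysis because the endpoints matter and the repair is cheap. There is no evidence that any result has been affected.

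**What to change.** - In protocol 7.1.2(d) and 7.1.3.4(d), correct the inequality to match the direction of SAP 2.9.1.3(d), and word the hematocrit limb so that it reads the same way.
- State that the corrected criterion (d) applies in both documents. Confine the statement to that criterion and do not make the SAP text govern the whole REPLACE-2 Major definition.
- Write the corrected REPLACE-2 Plus Major criteria into the SAP.
- Reconcile the non-CABG restriction between the protocol Synopsis, protocol 7.1.2 and the SAP, for the composite and for the safety endpoint.
- Before database lock, derive or check REPLACE-2 Major and Plus status for all patients, including bleeds already recorded, from the collected hemoglobin, hematocrit, transfusion, bleeding-site and CABG data. Protocol 7.1.1 already has bleeding site and relation to CABG recorded on the case report form.

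The cost is two protocol lines, short SAP additions and a check that uses mostly existing data. Some no-site cases may need a data query to establish whether a site was looked for.

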7.1.3 Other Bleeding Definitions

While not part of the primary safety analysis and composite endpoint, bleeding will be evaluated using alternate definitions as described below.

7.1.3.1 TIMI Major Bleeding Definition

Major bleeding is defined using the criteria from the trials of Thrombolysis in Myocardial Infarction (TIMI criteria). Major bleeding is defined as follows [64]:

- a. if there was a reduction of hemoglobin of 5 g/dl or more (or >15% in hematocrit); or
- b. any intracranial bleeding.

The TIMI Major bleeding definition takes into account blood transfusions, so that hemoglobin and hematocrit values are adjusted by 1 g/dl or 3%, respectively, for each unit of blood transfused.

Therefore, the true change in hemoglobin or hematocrit if there has been an intervening transfusion between two blood measurements is calculated as follows [68]:

Δ Hemoglobin = [baseline Hgb - post-transfusion Hgb] + [number of transfused units];

Δ Hematocrit = [baseline Hct - post-transfusion Hct] + [number of transfused units x 3].

7.1.3.2 TIMI Minor Bleeding Definition

Minor bleeding is defined using the criteria from the trials of Thrombolysis in Myocardial Infarction (TIMI criteria). Minor bleeding is defined as follows [64]:

- a. If there is an observed blood loss and a drop in hemoglobin of 3 to 5 g/dl (or in hematocrit from 10% to 15%) from study entry to the time of the lowest hemoglobin (hematocrit); or
- b. if there was spontaneous gross hematuria or hematemesis (>120 mL), even if the hemoglobin or hematocrit drop was less than 3 g or less than 10%, respectively; or
- c. if there was an unobserved blood loss 4 g/dl or more in hemoglobin or 12% or more in hematocrit.

The TIMI Minor bleeding definition takes into account blood transfusions, so that hemoglobin and hematocrit values are adjusted by 1 g/dl or 3%, respectively, for each unit of blood transfused.

Therefore, the true change in hemoglobin or hematocrit if there has been an intervening transfusion between two blood measurements is calculated as follows [68]:

Δ Hemoglobin = [baseline Hgb - post-transfusion Hgb] + [number of transfused units];

Δ Hematocrit = [baseline Hct - post-transfusion Hct] + [number of transfused units x 3].

7.1.3.3 REPLACE-2 Minor Bleeding Definition

Minor bleeding is defined as any observed bleeding event that does not meet the criteria for a major hemorrhage.

7.1.3.4 REPLACE-2 Plus Major Bleeding Definition

REPLACE-2 Plus Major bleeding is defined using criteria from the REPLACE-2 trial, with the exception of transfusion. REPLACE-2 Plus Major bleeding is defined as follows:

- a. any transfusion of whole blood or packed red blood cells, or
- b. intracranial hemorrhage, or
- c. retroperitoneal hemorrhage, or
- d. a fall in Hgb < 4 g/dL (or 12% of Hct) with no bleeding site identified despite attempts to determine, or
- e. spontaneous or non-spontaneous blood loss associated with a Hgb drop >3 g/dL (or 10% of Hct) with an overt site of hemorrhage.

The REPLACE-2 Plus Major bleeding definition takes into account blood transfusions, so that hemoglobin and hematocrit values are adjusted by 1 g/dl or 3%, respectively, for each unit of blood transfused.

Therefore, the true change in hemoglobin or hematocrit if there has been an intervening transfusion between two blood measurements is calculated as follows [68]:

Δ Hemoglobin = [baseline Hgb - post-transfusion Hgb] + [number of transfused units];

Δ Hematocrit = [baseline Hct - post-transfusion Hct] + [number of transfused units x 3].

7.1.3.5 TIMI Plus Major Bleeding Definition

TIMI Plus Major bleeding is defined using the criteria from the trials of Thrombolysis in Myocardial Infarction (TIMI criteria) with the exception of transfusion [64]:

- a. any transfusion of whole blood or packed red blood cells, or
- b. if there was a reduction of hemoglobin of 5 g/dl or more (or >15% in hematocrit); or
- c. any intracranial bleeding.

The TIMI Plus Major bleeding definition takes into account blood transfusions, so that hemoglobin and hematocrit values are adjusted by 1 g/dl or 3%, respectively, for each unit of blood transfused.

Therefore, the true change in hemoglobin or hematocrit if there has been an intervening transfusion between two blood measurements is calculated as follows [68]:

Δ Hemoglobin = [baseline Hgb - post-transfusion Hgb] + [number of transfused units];

Δ Hematocrit = [baseline Hct - post-transfusion Hct] + [number of transfused units x 3].

7.2 Thrombocytopenia

If a platelet count falls below 100,000 cells/ μ L and decreases at least 25% from the baseline value in any sample compared to any previous sample, additional repeat platelet

counts and/or further laboratory analyses (i.e., microscopic) per local institution guidelines must be performed to exclude laboratory error (clumping, etc.). The repeat platelet counts should be performed according to the specific practice at each institution. See Appendix 7 for guidelines for management of thrombocytopenia.

7.2.1 Moderate Thrombocytopenia

Moderate thrombocytopenia is defined as a platelet count <50,000 cells/ μ L.

7.2.2 Severe Thrombocytopenia

Severe thrombocytopenia is defined as a platelet count <20,000 cells/ μ L.

8.0 ADVERSE EVENTS

8.1 Definitions

An adverse event (AE) is any untoward new medical problem or exacerbation of an existing problem, experienced by a patient while enrolled in the study, whether or not it is considered drug-related by the Investigator.

Expected complications of percutaneous procedures as well as study endpoints that are not felt to be related to study drug are not to be considered adverse events, although any bleeding endpoint will still be recorded.

In addition, planned hospital admissions and/or surgical operations for an illness or disease which existed before the drug was given or the patient was randomized in a clinical study are not to be considered adverse events.

A serious adverse event (SAE) is any adverse event occurring within 48 hours that:

- Results in death; or
- Is life threatening (places the patient, in the opinion of the Investigator, at immediate risk of death from the experience as it occurred. [This does not include an adverse event that, had it occurred in a more severe form, might have caused death.]); or
- Results in a persistent or significant disability/incapacity (substantial disruption of one's ability to conduct normal life functions); or
- Results in or prolongs an existing in-patient hospitalization (hospitalization is defined as an in-patient admission, regardless of length of stay, even if the hospitalization is a precautionary measure for continued observation); or
- Is a congenital anomaly/birth defect (in offspring of patient taking the product regardless of time to diagnosis); or
- Is medically significant: requires medical or surgical interventions to prevent one or more of the outcomes above.

8.2 Study Drug Causality

The relationship of an AE to treatment will be assessed by the Investigator as one of the following:

- **Probably related:** There is a reasonable causal relationship between the study drug and the AE. The event responds to de-challenge.
- **Possibly related:** There is a reasonable causal relationship between the study drug and the AE.
- **Unlikely related:** There is not a temporal or causal relationship to the study drug administration.

